#### **7.4.3.6. Regulatory Reporting Requirements for SAEs**

Prompt notification by the investigator to GSK of SAEs related to study treatment (even for non- interventional post-marketing studies) is essential so that legal obligations and ethical responsibilities towards the safety of participants and the safety of a product under clinical investigation are met.

GSK has a legal responsibility to notify both the local regulatory authority and other regulatory agencies about the safety of a product under clinical investigation. GSK will comply with country specific regulatory requirements relating to safety reporting to the regulatory authority, Institutional Review Board (IRB)/Independent Ethics Committee (IEC) and investigators.

Investigator safety reports are prepared for suspected unexpected serious adverse reactions according to local regulatory requirements and GSK policy and are forwarded to investigators as necessary.

An investigator who receives an investigator safety report describing a SAE(s) or other specific safety information (e.g., summary or listing of SAEs) from GSK will file it with the IB and will notify the IRB/IEC, if appropriate according to local requirements.

#### **7.4.3.7. Cardiovascular and Death Events**

Investigators will be required to fill out the specific CV event page of the eCRF for the following AEs and SAEs:

Myocardial infarction/unstable angina

Congestive heart failure

Arrhythmias

Valvulopathy

Pulmonary hypertension

Cerebrovascular events/stroke and transient ischemic attack

Peripheral arterial thromboembolism

Deep venous thrombosis/pulmonary embolism

Revascularisation

For any cardiovascular events detailed above, whether or not they are considered SAEs, and all deaths, specific Cardiovascular (CV) and Death sections of the eCRF will be required to be completed. These sections include questions regarding cardiovascular (including sudden cardiac death) and non-cardiovascular death.

The CV CRFs are presented as queries in response to reporting of certain CV MedDRA terms. The CV information should be recorded in the specific cardiovascular section of the eCRF within one week of receipt of a CV Event data query prompting its completion.

#### **7.4.3.8. Death Events**

The Death CRF is provided immediately after the occurrence or outcome of death is reported. Initial and follow-up reports regarding death must be completed within one week of when the death is reported.

In addition, all deaths will require a specific death data collection tool to be completed. The death data collection tool includes questions regarding cardiovascular (including sudden cardiac death) and noncardiovascular death.

Adverse events that occur during the trial should be evaluated by the investigator and graded according to the Division of Acquired Immunodeficiency Syndrome (DAIDS) toxicity scales (see [Appendix 2](#)). Additional information regarding detecting, documenting and reporting AEs and SAEs are available in [Section 7.4.3.2](#). and [Section 12.6](#).

#### **7.4.3.9. Treatment Interruption Due to an Adverse Event**

IP may be interrupted at the discretion of the investigator and according to the severity of the AE. If one or more ART medication is held due to toxicity or AEs, all ART medications should be held to reduce the risk of development of resistance taking into account the length of the planned interruptions and the PK half-life of each ART of the regimen, in order to minimize the risk of development of resistance.

No toxicity-related dose reductions of IP will be allowed. IP should be restarted as soon as medically appropriate; in general, for oral dosing, this should be no longer than 14 days after discontinuation (unless Grade 3 or 4 toxicities persist). Any interruption in therapy during the Maintenance Phase, oral dosing, of greater than 7 consecutive days must be discussed with and agreed by the Medical Monitor prior to resumption of therapy. The Medical Monitor must be contacted upon becoming aware of resumption in therapy, if therapy was resumed without prior approval ([Section 6.9](#)). **IM dosing is expected to occur during the week in which the participant's projected visit falls (as according to the Day 1 visit). An additional (+ or -) 7 day window, from the projected visit date, is allowable for IM dosing but not preferred.** Any interruption

outside of this guidance **MUST** be discussed with the Medical Monitor prior to reinitiating IM IP (see Section 6.9.1).

Guidance is provided below on general participant management and IP interruptions based on the severity of the AE. Information regarding permitted substitutions \ is provided in Section 6.8. All changes in the IP regimen must be accurately recorded in the participant's eCRF.

**Note:** For participants receiving an ABC-containing product as part of the background regimen, in the event of a discontinuation of ABC for any reason, reinitiation of this drug should be undertaken with caution. The investigator should obtain a complete history of the events surrounding the discontinuation of the ABC-containing product, evaluate for the possibility of a clinically suspected HSR, and initiate participant management as outlined in the Local Country Prescribing Information, regardless of a participant's *HLA-B\*5701* status. Screening for the presence of *HLA-B\*5701* is recommended prior to reinitiating treatment with ABC-containing products in participants of unknown *HLA-B\*5701* status who have previously tolerated ABC but is not required to confirm study eligibility.

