## 4. STUDY DESIGN

### 4.1. Overall Design

201585 (ATLAS) is a Phase III, randomized, open-label, active-controlled, multicenter, parallel-group, non-inferiority study designed to assess the antiviral activity and safety of a two drug regimen of CAB LA + RPV LA compared with maintenance of current ART. Approximately 570 adult HIV-1 infected patients who are on a stable ARV regimen containing 2 NRTIs plus an INI, NNRTI, or a PI will be randomized 1:1 to continue current ART or be switched to the CAB LA + RPV LA regimen through 52 weeks. The study will continue with an Extension Phase up to at least 96 weeks.

Participants will be randomized (1:1) at Day 1 to either continue on current ART or to discontinue current ART and begin oral therapy with CAB 30 mg + RPV 25 mg once daily to determine individual safety and tolerability, prior to administration of CAB LA + RPV LA. Current ART dosing on Day 1 is recommended to occur after randomization to avoid overlap of regimens (in the event that the participant is assigned to the CAB LA + RPV LA treatment arm). However, if the participant takes current ART prior to coming into the clinic, randomization and initiation of oral CAB and RPV should continue as planned for Day 1.

For those randomized to receive CAB + RPV, at the Week 4a visit safety assessments (including e.g., clinical chemistries) will be performed as per the Time and Events Table (Section 7.1). At visit Week 4b, participants will return to the clinic, take the last dose of oral CAB + RPV, and receive the first CAB LA (600 mg) + RPV LA (900 mg) injections (within 2 hours of the final oral dose of CAB + RPV). The first injection visit (Week 4b) can be performed once central lab results are available and safety parameters are reviewed. If a retest is required based on Week 4a labs, the retest should be performed as soon as possible (and preferably no later than 7 days following Week 4a). Participants will remain on oral CAB 30 mg + RPV 25 mg until the Week 4b injection visit, and until any required Visit 4a retest results are available for review. The visit schedule following the oral lead-in phase will be based on timing of the first injection visit at Week 4b such that the Week 5 visit should be performed approximately 7 days after the Week 4b visit.

[figure not shown]

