Participants with a Week 48 HIV-1 RNA <50 c/mL, will initiate a 4 week lead-in of oral CAB 30 mg + oral RPV 25 mg once daily at Week 52. Clinical chemistries will also be assessed. At Week 56a, following the 4 week CAB + RPV oral lead-in, participants will have additional safety assessments including clinical chemistries as per the Time and Events Table (Section 7.1). In addition, central lab results and safety parameters from the Week 56a visit must be available and reviewed before the Week 56b visit. If a clinical chemistry retest is required based on the Week 56a labs, the retest should be performed as soon as possible (and preferably no later than 7 days following Week 56a). Participants will remain on oral CAB 30 mg + RPV 25 mg until the Week 56b injection visit, and until any required Visit 56a retest results are available for review.

At visit Week 56b, participants will return to the clinic, take the last dose of oral CAB + RPV, and receive the first CAB LA + RPV LA injections (within 2 hours of the final oral dose of CAB + RPV). The Week 56b visit can be performed as soon as central lab results from the Week 56a visit become available and safety parameters are reviewed. If a retest is required based on Week 56a labs, the retest should be performed as soon as possible (and preferably no later than 7 days following Week 56a). Participants will remain on oral CAB 30 mg + RPV 25 mg until the Week 56b injection visit, and until any required Visit 56a retest results are available for review. The visit schedule for the Extension Phase following the oral lead-in phase will be based on timing of the first injection visit at Week 56b. The second and third IM injections with CAB LA 400 mg and RPV LA 600 mg will be performed at Week 60 and Week 64. There will be a one

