**Table 2 Proportion (95% CI) of Participants with Plasma HIV-1 RNA <50 c/mL at Week 48 - Snapshot (MSDF) Analysis (ITT-E Population) in LATTE-2**

Outcome	Q8W IM N=115 n (%)	Q4W IM N=115 n (%)	Q8W+Q4W N=230 n (%)	CAB 30 mg N=56 n (%)
Virologic Success, n (%)	106 (92)	105 (91)	211 (92)	50 (89)
Virologic Failure, n (%)	8 (7)	1 (<1)	9 (4)	1 (2)
Data in window not below threshold	6 (5)	1 (<1)	7 (3)	0
Discontinued for lack of efficacy	1 (<1)	0	1 (<1)	1 (2)
Discontinued for other reason while not below threshold	1 (<1)	0	1 (<1)	0
No Virologic Data	1 (<1)	9 (8)	10 (4)	5 (9)
Discontinued due to AE or Death	0	6 (5)	6 (3)	2 (4)
Discontinued for Other Reasons	1 (<1)	3 (3)	4 (2)	3 (5)

CAB LA and RPV LA were both well tolerated resulting in a low discontinuation rate due to AEs, including injection site reaction (ISR) related AEs, with no significant trends in safety parameters in either the Q8W or Q4W dosing regimens.

Due to the increased Snapshot failure rate at Week 48 for the Q8W Arm, a Q4W dosing strategy was selected for further evaluation in Phase 3. To allow some flexibility, with the exception of Week 8 and Week 12, a one-week window (on each side) around the 4-weekly dosing regimen can be allowed following Week 12 (third injection), without anticipated impact on the safety or efficacy of the regimen. For Week 8 and Week 12, there is only a minus one week window such that injections should be administered no later than Week 8 and Week 12.

For CAB LA, steady-state mean CAB pre-dose concentrations following Q4W dosing remain between the oral CAB 10 mg and 30 mg once daily mean trough concentrations, which were both doses found to be safe and efficacious in the LATTE study. For RPV LA, steady-state mean RPV pre-dose concentrations following Q4W dosing are comparable with the range of exposures following oral RPV 25 mg once daily observed to be safe and efficacious in pivotal Phase 3 studies. Maintenance Phase PK data in LATTE 2 are summarized for both regimens of CAB LA (Table 3, Figure 2) and RPV LA (Table 4, Figure 3).

**Table 3 Summary of Observed PK Parameters following Repeat Dose Administration of Cabotegravir LA to HIV-infected Participants (LATTE-2)**

Cohort	Plasma CAB PK Parameter a							
	AUC(0- $\tau$ ) b ( $\mu\text{g}\cdot\text{h}/\text{mL}$ )		C max c ( $\mu\text{g}/\text{mL}$ )		Individual Average C 0 d ( $\mu\text{g}/\text{mL}$ )		t max e (d)	

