### **6.3. Dosage and Administration**

Participants will be randomly assigned to receive treatment with Oral CAB 30 mg + RPV 25 mg once daily for 4 to 5 weeks during the Oral Phase, followed by CAB LA 600mg + RPV LA 900mg IM at Week 4b, CAB LA 400mg + RPV LA 600 mg IM at Week 8 and Q4 weekly thereafter, or to remain on their current ART. Regardless of treatment arm assignment, the investigator should instruct all participants on the importance of treatment adherence. This study has an open-label design. Dosing is outlined in [Table 5](#) below.

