**It is important to note that keeping to the participant’s visit schedule is a very important component to the study.**

**Note: All decisions regarding dose interruption / resumption must be discussed with the medical monitor in advance.**

### **6.9.1. IM Dosing**

Participants receiving CAB LA and/or RPV LA are anticipated to be at risk for development of virologic resistance if ART is interrupted. The time period during which participants are at risk for development of virologic resistance may be determined by the period between when drug levels fall below therapeutic values and when they fall below levels which exert selective pressure on HIV. This time period will vary by ART agent and is dependent upon effective concentration, inhibitory concentration, and half-life. Plasma concentrations of both LA drugs may be measurable for more than one year following IM injections. Any interruption in IM dosing should be discussed with the Medical Monitor. Investigators should ensure that the participant initiates alternative highly active ART to minimize the risk of developing resistance as concentrations of CAB and RPV decline over time.

IM dosing is expected to occur during the week in which the participant’s projected visit falls (as according to the date of the first injection). The first injections are administered at Week 4b (can be performed as soon as lab results from Week 4a become available), and the second injections are given at Week 8. The dosing window for the second injections allows administration between Week 7 and Week 8, but not later than Week 8. The dosing window for the third injections allows administration between Week 11 and

Week 12 but not later than Week 12. For subsequent injection visits, an additional (+ or -) 7 day window, from the projected visit date, is allowable for IM dosing but also not preferred. In addition, starting after the Week 12 injection, efforts should be made to limit time between injection visits to a maximum of 5 weeks. The Medical Monitor must be contacted if the length of time between injections exceeds or is projected to exceed 5 weeks. For the duration of the study, the injection visit schedule should be maintained according to the first IM injections given at Week 4b.

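### Section 7.4.3.9 projects injection visits from Day 1 with a flat ±7-day window, against the first-injection anchor and the tighter early windows set elsewhere in the protocol

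*Protocol*

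**What the plan says.** Section 7.4.3.9, in bold operative text, places IM dosing in the week of the projected visit and names the Day 1 visit as the reference point: "projected visit falls (as according to the Day 1 visit". It then allows a further 7 days either side for IM dosing, with no exception for the early injections. Interruptions beyond that guidance go to the Medical Monitor, with a pointer to Section 6.9.1.

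The rest of the protocol uses a different reference point:

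- Section 6.9.1: "projected visit falls (as according to the date of the first injection", and for the duration of the study "the injection visit schedule should be maintained according to the first IM injections given at Week 4b".
- Section 4.1: the schedule after the oral lead-in "will be based on timing of the first injection visit at Week 4b".
- Section 4.2.3.2, for control-arm participants who switch: the schedule "will be based on timing of the first injection visit at Week 56b".

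It also sets a one-sided window for the early injections. For the second, Section 6.9.1 "allows administration between Week 7 and Week 8, but not later than Week 8", and a matching limit applies to the third at Week 12. Section 4.7.2 says of both that "there is only a minus one week window such that injections should be administered no later than Week 8 and Week 12". The PK visit windows in Section 7.5.1 likewise give minus 7 days only for these two visits.

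Section 6.3 gives oral CAB + RPV "once daily for 4 to 5 weeks during the Oral Phase", so the gap between Day 1 and the first injection is not fixed.

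**The concern.** The two anchors agree only when the lead-in is exactly 28 days. With a longer lead-in, a site that takes the due date from Section 7.4.3.9 projects every later injection too early. For a control-arm participant who switches, Day 1 lies about 56 weeks before the first injection, so it is no sensible reference at all.

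The flat ±7 days is a separate fault that does not depend on the anchor. It reopens the late edge that the protocol closes for the second and third injections. The one-week-delay simulations shown in Section 4.7.3 are at steady state (Week 40 moved to Week 41). Section 4.7.3.2 predicts a median RPV trough of 42 ng/mL four weeks after the loading dose, against 86.8 ng/mL at steady state. The protocol shows no simulation that supports a late second injection.

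Section 7.4.3.9 is where a site looks when an adverse event has disturbed dosing, so a wrong rule there can be acted on.

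**Working it through.** **Convention.** Days are counted from Day 1, with Week k = 7k. Let L be the day of the first injection: L = 28 after a 4-week lead-in and L = 35 after a 5-week lead-in (Section 6.3).

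**Offset between the anchors.** Offset = L − 28, which is 0 days at L = 28 and 7 days at L = 35. The upper value equals one full side of the ±7-day window, and the offset carries to every later injection.

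**Second injection (Week 8).**

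- Section 7.4.3.9: 56 ± 7 = days 49 to 63, which is 49 − L to 63 − L days after the loading dose.
- Section 6.9.1: due on day L + 28, minus 7 days only, which is 21 to 28 days after the loading dose whatever the value of L.

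**Fourth injection (Week 16), where Section 6.9.1 also allows ±7 days.**

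- Section 7.4.3.9: 112 ± 7 = days 105 to 119.
- Section 6.9.1: (L + 84) ± 7.

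| Lead-in | Injection | Section 7.4.3.9 | Section 6.9.1 |
|---|---|---|---|
| 4 weeks (L = 28) | Second | days 49–63 (21–35 after loading) | days 49–56 (21–28 after loading) |
| 4 weeks (L = 28) | Fourth | days 105–119 | days 105–119 |
| 5 weeks (L = 35) | Second | days 49–63 (14–28 after loading) | days 56–63 (21–28 after loading) |
| 5 weeks (L = 35) | Fourth | days 105–119 | days 112–126 |

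After a 4-week lead-in the anchors coincide, and the only error is the late edge of the second injection: 35 − 28 = 7 days too long. After a 5-week lead-in the late edge of the second injection happens to match, but its early edge is 21 − 14 = 7 days too soon. The late edge for the fourth injection is 126 − 119 = 7 days short.

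**Could Day 1 mean the day of the first injection?** That usage occurs in the dose-conversion text of Section 4.7.2 and the simulation figure notes of Section 4.7.3. It does not fit Section 7.4. Section 7.4.4.13 treats Day 1 and Week 4b as the two ends of an interval, and Section 7.4.9 equates Day 1 with Baseline. Where the protocol does intend a Baseline anchor for visits, in Section 6.9.2, it applies it to oral dosing. Even if the alternative reading were accepted, the missing limit on the second and third injections would remain.

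**The case against.** The strongest reply is that other text contains the damage.

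- **Safeguards.** Section 7.4.3.9 itself points to Section 6.9.1. Sections 6.9.1 and 6.9.2 carry prominent notes that interruption and resumption decisions go to the Medical Monitor beforehand. The Study Procedures Manual gives scheduling examples, and the Week 8 and Week 12 limits appear in several other sections. This stands and is why the point is minor. It does not make the stated rule correct.
- **Section 6.9.1 uses the same shorthand.** One of its bullets allows dosing without consultation within ±7 days. This is true, but that bullet follows the specific limits for the early injections, whereas Section 7.4.3.9 states no such limits. The bullet should be borne in mind when making the fix.
- **The 7-day offset is the extreme.** It needs a full 5-week lead-in. Section 7.5.1 gives ±3 days around the projected first-injection visit, and Section 4.1 mainly allows more time when Week 4a laboratory tests must be repeated. This also stands: many participants would have an offset near zero. For them, though, the late-edge error for the second injection is at or near its largest.
- **Early dosing is less worrying, and unlikely after an interruption.** This is fair for the 14-day case, and the protocol shows no harm from early dosing. But if late resumption is the realistic risk in this section, the 35-day late edge matters more.

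**Conclusion.** The concern holds. Section 7.4.3.9 states the wrong anchor for injection visits and omits the limit on the second and third injections. The anchor error is 0 to 7 days over the stated 4- to 5-week lead-in. For the second injection, the window starts up to 7 days too early after a 5-week lead-in and ends up to 7 days too late after a 4-week one. These figures assume that a site reads Section 7.4.3.9 on its own and that Day 1 means the Baseline visit, as it does elsewhere in Section 7.4. The consequence is operational and minor. Section 6.9.1 governs, and the primary analysis, sample size and type I error are not affected.

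**What to change.** In Section 7.4.3.9, replace the reference to the Day 1 visit with the date of the first injection (Week 4b, or Week 56b for participants who switch in the Extension Phase). Replace the ±7-day sentence with a reference to the dosing windows in Section 6.9.1. At the same time it would help to make the general ±7-day bullet in Section 6.9.1 expressly subject to the Week 8 and Week 12 limits, and to the Week 60 and Week 64 limits for participants who switch, since the new cross-reference leads readers there. The core change is one phrase and one cross-reference in one section, at no cost to the trial.

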#### **7.4.3.10. Grade 1 or Grade 2 Toxicity/Adverse Event**

Participants who develop a Grade 1 or Grade 2 AE or toxicity may continue study drug at the discretion of the investigator. Participants who choose to withdraw from the study due to a Grade 1 or 2 AE should have study withdrawal and follow-up evaluations completed.

**Participants who develop ALT  $\geq$ 3 times ULN while on study must consult with Medical Monitor prior to initiation or continuation of CAB LA + RPV LA**

#### **7.4.3.11. Grade 3 Toxicity/Adverse Event**

Participants who develop a Grade 3 AE or toxicity should be managed as follows:

- If the Investigator has compelling evidence that the Grade 3 AE or toxicity has not been caused by IP, dosing may continue after discussion with the Medical Monitor.
- Participants who develop a Grade 3 AE or toxicity, which the Investigator considers related or possibly related to the IP, should have the IP withheld and be rechecked each week until the AE returns to Grade 2. Once the AE is Grade  $\leq$ 2, IP may be re-started.
- Should the same Grade 3 AE recur within 28 days in the same participant, the IP should be permanently discontinued and the participant withdrawn from study.
- Participants experiencing Grade 3 AEs requiring permanent discontinuation of IP should be followed weekly until resolution of the AE and to have withdrawal study evaluations completed. A follow-up visit should be performed 4 weeks after the last dose of IP. Any participant receiving at least one dose of CAB LA

and /or RPV LA who discontinue IP / Withdraw will initiate treatment with HAART and enter the Long-Term Follow-Up Phase for 52 weeks of follow up.

- Participants with Grade 3 asymptomatic laboratory abnormalities should be investigated for all potential non-drug related causes, and, following discussion with the Medical Monitor, may continue IP if the Investigator has compelling evidence that the toxicity is not related to IP, with the exception of liver chemistry stopping criteria (See Section 7.4.4.1). Isolated Grade 3 lipid abnormalities do not require withdrawal of IP.

